Venous thromboembolism (VTE) is a common, potentially life-threatening complication in high-risk trauma patients. With emerging evidence demonstrating around 50% of trough serum anti-factor Xa (anti-Xa) concentrations are subtherapeutic and associated with increased VTE risk, the purpose of this pilot study is to evaluate the safety and efficacy of a novel enoxaparin dosing strategy based on anti-Xa values. High-risk patients (e.g., risk assessment profile score ≥ 5) initiated on enoxaparin 30 mg q12h per current trauma team standard of care. Patients will be excluded for renal dysfunction (Cockcroft-Gault calculated creatinine clearance < 30 mL/min or patients on continuous renal replacement therapy), weight < 50 kg or > 150 kg, nephrotic syndrome, platelet count $< 50 \times 10^3$, allergy to heparin, patients on or requiring therapeutic anticoagulation at or within 24 hours of admission, isolated intracranial hemorrhage, known hyperbilirubinemia, pregnancy, or incarceration. Primary outcome is the comparison of antithrombin-III (AT-III), proportion of anti-Xa goal achievement at first, second, and all assessments, and time to goal anti-Xa. Patient outcomes include VTE events, bleeding outcomes, patients with bioaccumulation, and risk factors for low anti-Xa.

Purpose of Study

The purpose of this pilot study is to compare two enoxaparin dosing strategies: BID dosing and a dosing strategy based on anti-Xa values in high-risk trauma patients. Specific aims include: 1) to compare the extent of reduced AT-III activity between patients with anti-Xa ≥ 0.1 IU/mL and < 0.1 IU/mL upon initial assay and determine the proportion of patients who reach goal anti-Xa and time to goal anti-Xa between two dosing strategies: enoxaparin 40 mg every 12 hours (with consideration to increase to 50 mg every 12 hours if recheck anti-Xa is not at goal; see section 6) and enoxaparin 30 mg every eight hours; 2) to compare anti-Xa adjusted enoxaparin-dosing strategies based on VTE, bleeding rates, transfusion requirements, drug discontinuation rate and bioaccumulation, and 3) to determine patient-specific factors that correlate to subtherapeutic anti-Xa such as serial AT-III activity, weight, body mass index, age, cumulative fluid administration and thromboelastography (TEG).

Background

Background and Significance

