Increased VTE rates have been seen in patients with subtherapeutic anti-Xa values. Malinoski¹⁵ found that of 54 patients on enoxaparin 30 mg every 12 hours, 27 (50%) had subtherapeutic anti-Xa troughs and a statistically significant higher DVT rate than those with appropriate levels (37% vs. 11%, $p = 0.026$). Mean peak anti-Xa values were also lower in the subtherapeutic group (0.17 ± 0.1 IU/mL vs. 0.27 ± 0.1 IU/mL, $p < 0.001$); however, peak anti-Xa values were not different in those with and without DVT (0.23 ± 0.12 IU/mL vs. 0.23 ± 0.1 IU/mL, $p = \text{NS}$). A subsequent enoxaparin anti-Xa dose-adjusted protocol targeting peak anti-Xa levels between 0.2 – 0.4 IU/mL showed 18 (29.5%) of 61 patients on 30 mg twice-daily enoxaparin were at goal anti-Xa after the third dose.¹⁶ Only 5 (8.2%) patients, all in the therapeutic peak anti-Xa group, had a trough anti-Xa > 0.1 IU/mL. VTE events occurred in three patients in the entire study cohort (4.9%). Of the 27 patients with dosage adjustments, 22 (81.5%) patients received enoxaparin 40 mg twice daily, four patients received 50 mg twice daily (14.8%), and 1 patient received 60 mg twice daily (3.7%). Of note, there were no major bleeding events, which is not surprising given the anti-Xa peak goal is much lower when compared to standard therapeutic dosing goals (e.g., 0.5 – 1.1 IU/mL). Finally, a before-and-after study evaluated an anti-Xa adjusted dalteparin dosing strategy in high-risk (risk assessment profile [RAP] ≥ 5) trauma patients.¹⁷ High-risk patients were initiated on dalteparin 5000 units daily with a 12-hour anti-Xa value drawn after the first dose in the post-protocol group. If the 12 hour anti-Xa was < 0.1 IU/mL, the dose was increased to 5000 units twice-daily. Low trough anti-Xa was seen in 51% of post-group patients. VTE was lower in the post-protocol group (7.0% vs. 12.8%, $p = 0.009$) and higher in the subgroup of patients with a subtherapeutic trough anti-Xa (14.4% vs. 5.4%, $p = 0.05$). Therefore, anti-Xa adjustment of LMWH may result in fewer VTE events. No difference in blood transfusion after the first 48 hours was noted, suggesting appropriate safety with an anti-Xa driven dosing protocol for dalteparin.

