Robinson ¹⁴ (1 mg/kg q24h; n = 19)	0.40	-	-	-	-

Study Justification

Ideal enoxaparin dose for VTE prevention in high-risk trauma patients is unknown. Predictors and explanations for low anti-Xa are also unknown. With emerging evidence demonstrating around 50% of trough anti-Xa concentrations are subtherapeutic and associated with increased VTE risk, the purpose of this study is to compare AT-III serum concentrations as a predictor of low anti-Xa. Secondly, the study will compare two enoxaparin dosing. Ultimately, this information can be used to develop an optimum protocol for patient-specific enoxaparin dosing for VTE prevention to improve patient outcomes.

METHODS**Study design**

This is an investigator-initiated, single-center, prospective, non-blinded, randomized controlled trial. Multi-system trauma patients between 18-80 years old admitted to the University of Cincinnati Medical Center (UCMC), an urban American College of Surgeons-verified Level 1 trauma center will be identified by the Trauma Surgery team. The trauma team will inform study personnel of these patients once enoxaparin is initiated. These patients will be screened for inclusion in the study. Patients who meet inclusion criteria will be administered informed consent by study personnel in their rooms. Patients in the surgical intensive care unit (SICU) and on the surgical floor are eligible for enrollment if all other inclusion and exclusion criteria are met. Informed consent will be obtained prior to enrollment. Goal enrollment is 200 patients with 100 patients in the control group and 50 patients in each randomization group.

Research data collection/study procedures

Patients will be screened daily by the trauma team. Research personnel will be alerted to potential patients for enrollment.

Intervention

Serum AT-III and anti-Xa will be drawn eight hours after the third dose of enoxaparin 30 mg q12h. Serum assays after at least the third dose should approximate drug steady state trough concentrations. Patients with a serum anti-Xa ≥ 0.1 IU/mL will remain on enoxaparin 30 mg every 12 hours and will be the control group. Patients with undetectable anti-Xa (intervention groups), defined as a trough anti-Xa < 0.1 IU/mL, will be randomized to receive either:

- a. Enoxaparin 40 mg every 12 hours (group 1)
- b. Enoxaparin 30 mg every eight hours (group 2)

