2. Proportion of patients reaching goal anti-Xa between group 1 and group 2 overall, at first repeat assessment, and at second repeat assessment.
3. Median time to achievement of goal anti-Xa between group 1 and group 2.

Secondary Endpoints

1. Patient outcomes to be compared between control and intervention groups including all VTE events (i.e., pulmonary embolism; upper extremity deep venous thromboembolism [DVT]; proximal lower extremity DVT; distal lower extremity DVT), major bleeding (i.e., hemoglobin decrease of ≥ 2 g/dL in a 24 hour period requiring ≥ 2 units of packed red blood cells while on enoxaparin; worsened or new intracranial hemorrhage while on enoxaparin; repeat surgical intervention due to hemorrhage while on enoxaparin), minor bleeding (minor gastrointestinal bleeding [coffee ground emesis with or without < 2 units packed red cell transfusion needed while on enoxaparin]; interruption of study drug by trauma team; other overt bleeding not characterized a major while on enoxaparin), total transfusion requirements after 48 hours until discharge or admission day 28.
2. Proportion of patients with enoxaparin bioaccumulation (defined as an anti-Xa ≥ 0.3 IU/mL at any assay) between group 1 and 2.
3. Risk factor determination for low anti-Xa.

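### VTE, bleeding and transfusion are compared with a control group selected on anti-Xa level, not between the two randomised regimens that Aim 2 sets out to compare

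*Combined protocol and SAP*

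**What the plan says.** In Purpose of Study, aim 1 names the two dosing strategies as 40 mg every 12 hours (with a possible increase to 50 mg) and 30 mg every eight hours. These are the two randomised groups. Aim 2 is then "to compare anti-Xa adjusted enoxaparin-dosing strategies based on VTE, bleeding rates, transfusion requirements, drug discontinuation rate and bioaccumulation".

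Under Data Analysis, Secondary Endpoints, item 1 reads "Patient outcomes to be compared between control and intervention groups including all VTE events", and goes on to list major and minor bleeding and transfusion requirements. Item 2, by contrast, names the randomised groups: "Proportion of patients with enoxaparin bioaccumulation (defined as an anti-Xa ≥ 0.3 IU/mL at any assay) between group 1 and 2". Goal attainment and time to goal, under Primary Endpoints, are also stated as group 1 vs group 2.

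The groups are defined under Intervention. Membership of control follows from the first assay alone: "Patients with a serum anti-Xa ≥ 0.1 IU/mL will remain on enoxaparin 30 mg every 12 hours and will be the control group". Chance allocation enters only on the other side of that threshold, where the section states "Patients with undetectable anti-Xa (intervention groups), defined as a trough anti-Xa < 0.1 IU/mL, will be randomized to receive either" and then lists the regimens of groups 1 and 2. Planned sizes are 100, 50 and 50.

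The statistical methods paragraph plans Fisher's exact or chi-square tests for nominal data, and t-test/ANOVA or rank-based equivalents for continuous data. The only regression planned is for risk factors for low anti-Xa.

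**The concern.** Control and intervention patients are separated by a laboratory value measured before allocation, and the protocol itself treats that value as a marker of VTE risk. Background and Significance reports DVT in 37% of patients with low trough anti-Xa against 11% of those with adequate levels, in a 54-patient cohort on 30 mg every 12 hours. It also reports VTE in 14.4% against 5.4% in a dalteparin study. A raw comparison of control with intervention therefore mixes the baseline difference in risk with whatever the new regimens do.

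The one comparison that randomisation protects, group 1 vs group 2, is not named for VTE, bleeding or transfusion. Followed as written, the plan could report an effective regimen as harmful, and it would leave Aim 2 unanswered for these outcomes. No baseline difference in bleeding or transfusion is documented, but the comparison is equally non-randomised for them.

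**Working it through.** **1. The plan's own figures.** The methods paragraph and Table 2 give alpha 0.05 and 80% power; two-sided tests reproduce the table.

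- AT-III, difference 10, SD 25: n per group = 2(1.96 + 0.84)² × 25²/10² ≈ 98.1, so 198 in total. The t-test version gives the stated 200.
- Goal anti-Xa, 50% vs 77%: 98 in total from the pooled two-proportion formula; stated 100.
- VTE rows, with n = [1.96√(2p̄q̄) + 0.84√(p₁q₁ + p₂q₂)]²/d² and the continuity correction n′ = (n/4)[1 + √(1 + 4/(nd))]²: 37% vs 11% gives 98, 14.5% vs 5.5% gives 390, and 5.5% vs 2.5% gives 1,468, all as stated.
- The last VTE row, 5.5% vs 4.5%, gives 15,308 (14,912 uncorrected), not 6,576. The figure 6,576 is exactly the result for 5.5% vs 4.0%. This is a minor, separate point.

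Table 2 enters 37% as control and 11% as intervention. In the cited cohort 37% belongs to low anti-Xa patients, who form this trial's intervention groups. The 14.5%/5.5% row closely matches the low/adequate split in the dalteparin study (14.4%/5.4%). The table thus treats control as the higher-risk group, while the design makes it the lower-risk one.

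**2. Control vs pooled intervention, 100 vs 100.** Assumption: the cited rates are the VTE risks without dose adjustment. Three pairs (low vs adequate anti-Xa) are used:

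- 37% vs 11%.
- 14.4% vs 5.4%.
- The ratio 37/11 scaled to the centre's 5.5% registry rate with equal strata: 2 × 5.5 × 37/48 = 8.48% vs 2.5 × 1.00833 = 2.52% (that is, 2 × 5.5 × 11/48).

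The reductions are illustrative, because the documents give no VTE effect for these regimens. The intervention risk is the low-stratum risk × (1 − reduction). Exact probabilities for a two-sided Fisher test at 0.05:

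| Reduction in VTE | 37 vs 11 | 14.4 vs 5.4 | 8.48 vs 2.52 |
|---|---|---|---|
| 0%: intervention significantly worse | 99% | 49% | 34% |
| 25%: significantly worse | 82% | 21% | 15% |
| 50%: significantly worse | 26% | 4.2% | 3.5% |
| 70%: significantly worse | 1.6% | 0.4% | 0.4% |
| 50%: significantly better | 0.01% | 0.29% | 0.08% |
| 50%: expected rates, intervention vs control | 18.5 vs 11 | 7.2 vs 5.4 | 4.2 vs 2.5 |

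Break-even reduction, below which intervention is expected to look worse: 1 − 11/37 = 70.3%; 1 − 5.4/14.4 = 62.5%.

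**3. Three-group reading, 100/50/50.** Exact test on the 3 × 2 table, groups 1 and 2 truly identical, 100,000 simulated trials. Share significant at reductions of 25%, 50% and 70%:

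- 37 vs 11: 80%, 26%, 4.9%.
- 14.4 vs 5.4: 25%, 7.9%, 4.1%.
- 8.48 vs 2.52: 24%, 10%, 3.7%.

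At 25% and 50%, nearly all of these results have intervention above control. The test therefore responds to the control stratum even when the two regimens do not differ.

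**4. Precision of group 1 vs group 2, 50 vs 50.** Half-width = 1.96√(2p(1 − p)/50): 8.9 points at 5.5%, 10.1 at 7.2%, 12.3 at 11%, 15.2 at 18.5%.

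Bleeding and transfusion cannot be sized, because the documents give no rates by anti-Xa level.

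**The case against.** The purpose statement is not of one mind. Its opening sentence sets twice-daily dosing against anti-Xa based dosing, which can be read as control vs adjusted dosing and so as the contrast in Secondary Endpoint 1. The plural in that endpoint may also mean three groups, so pairwise testing is unstated rather than ruled out. Both points stand as to wording. Neither makes control randomised, and an overall three-group test does not isolate group 1 vs group 2. ANOVA and Kruskal-Wallis are in any case planned for continuous data, so they would reach transfusion but not event counts.

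The size of the problem is uncertain, and this stands. The 37% vs 11% pair is DVT in one 54-patient cohort and marks the top of the range. In the dalteparin study, "If the 12 hour anti-Xa was < 0.1 IU/mL, the dose was increased to 5000 units twice-daily", so 14.4% may already include some benefit of adjustment. At the scaled registry rate with VTE halved, a false signal of harm appears in only 3.5% of trials. The expected direction is still wrong there.

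The randomised contrast has limits too. Patients removed for a change in creatinine after randomisation are left out of the VTE and bleeding analyses, so it will not be a full 50 vs 50. Nor can it show whether a raised dose causes more bleeding than the standard one. Control vs intervention bears on that question, but only observationally.

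Finally, these are secondary endpoints of a pilot, and the corrected comparison will be imprecise. That limits the severity but does not justify leaving a misleading comparison in the plan.

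**Conclusion.** The concern holds. Secondary Endpoint 1 specifies an unadjusted, non-randomised comparison for VTE, bleeding and transfusion, and no endpoint carries Aim 2's comparison of the two adjusted regimens on these outcomes. For VTE, under the assumptions in the working, the comparison is expected to favour control unless the regimens cut VTE by more than about 62.5% to 70%. The chance of a falsely significant harm at a 25% reduction runs from 15% to 82%. These figures depend on the cited rates being risks without dose adjustment; that the comparison is not randomised depends on no rate at all. The change should be made, but neither the primary endpoints nor the target of 200 is affected.

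**What to change.** In Secondary Endpoint 1, name group 1 vs group 2 as the comparison for VTE, bleeding and transfusion. Report risk differences for events, and mean or median differences for transfusion, each with a 95% confidence interval. Present the control stratum alongside as a descriptive, non-randomised reference, and state that differences from it are not interpreted as treatment effects. Report by group how many patients are left out for renal change. Aim 2 also lists drug discontinuation, which has no endpoint of its own (interruption of study drug appears only within minor bleeding); either add it to this comparison or drop it from the aim.

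Separately, correct either the rate or the N in the last VTE row of Table 2, after checking the source table for a misread digit.

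The cost is wording only, with no new data or patients. The price in interpretation is that intervals of roughly ±9 to ±15 points make the results mainly descriptive. The contrast compares two regimens with each other; it does not estimate adjustment vs no adjustment, because no patient with low anti-Xa is randomised to stay on the starting regimen.

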Previous studies have tried to identify predictors for low anti-Xa concentrations. Young age, high body weight, edema, and low peak anti-Xa concentration have been associated with low trough anti-Xa.^{11, 15, 17} AT-III concentrations have not been collected or evaluated in many previous studies. Low AT-III concentrations have not been evaluated as a risk factor for low anti-Xa. Theoretically, low serum AT-III may represent a reduction in substrate to which LMWH can bind and exert anticoagulant effects. Hence, LMWH effectiveness and anti-Xa may be reduced.

Pharmacokinetic / Safety Information

Previous pharmacokinetic studies evaluating enoxaparin prophylaxis and anti-Xa levels suggest high inter-patient variability, especially in critically ill patients (table 1).^{11-12,14} However, the mean maximum serum concentration (C_{max}) did not reach the lower threshold for therapeutic dosing. Therapeutic enoxaparin anti-Xa concentrations are between 0.5 – 1.1 IU/mL for 1 mg/kg every 12 hours, and 1.0 – 2.0 IU/mL for 1.5 mg/kg every 24 hours.¹⁹ No major bleeding events were identified in previous studies.^{12,14} Additionally, evaluation of anti-Xa adjusted dalteparin dosing found no difference in transfusion requirements.¹⁷ Other evaluations of enoxaparin have found few minor bleeding events such as hematoma following total hip arthroplasty, ecchymosis, hematuria, and epistaxis.^{10,20} Based on these previous pharmacokinetic evaluations, patients enrolled in the proposed study would achieve a steady state peak between 0.3 – 0.5 IU/mL and a steady state trough between 0.1 – 0.3 IU/mL. Maintenance of said anti-levels should prevent major bleeding events. Additionally, exclusion of patients with poor renal function, defined as a Cockcroft-Gault calculated creatinine clearance < 30 mL/min will reduce the risk of bleeding events due to reduced drug elimination.

Table 1. Previous pharmacokinetic analyses of enoxaparin.

Trauma Population	Cmax (IU/mL)	Trough (IU/mL)	Half-life (hours)	AUC ₀₋₁₂ (IU/L per hour)	Vd (mL/kg)
Non-Edematous* ¹¹ (30 q12h; n = 11)	0.27 (0.19-0.59)	-	1.67 (0.64-3.92)	1.57 (0.91-3.83)	45.8 (28.9-76.4)
Edematous* ¹¹ (30 q12h; n = 10)	0.12 (0.07-0.34)	-	0.68 (0.31-1.97)	0.63 (0.34-2.18)	43.9 (31.2-68.6)
Rutherford ¹² (40 mg q24h; n = 17)	0.195±0.088	0.044±0.043	-	-	-
Robinson ¹⁴ (40 mg q24h; n = 20)	0.13	-	-	-	-
Robinson ¹⁴ (30 mg q12h; n = 30)	0.15	-	-	-	-
Robinson ¹⁴ (40 mg q12h; n = 40)	0.33	-	-	-	-

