Droege ¹⁷	14.5%	5.5%	390
2013 UCMC Trauma Registry VTE	5.5%	2.5%	1468
2013 UCMC Trauma Registry VTE	5.5%	4.5%	6576

Data storage and confidentiality (include sample storage if applicable)

A single, central, electronic database will be constructed using Microsoft Excel® for storing all study-related data (attached). The database will be password protected such that only authorized study personnel can access the data. Data will be maintained in a confidential manner with regular reminders of the need for confidentiality provided from the senior investigator. A single subject log will be kept for matching patient study number, initials, medical record number, and admission date (attached). Once assigned to the log, patients will only be evaluated using their de-identified, study number. Data entered into the electronic database will be de-identified.

Once the study has been completed, the electronic database will be maintained in a locked office, per the IRB specifications. Only study personnel will have access to the data. Once the IRB-approved time has elapsed, all materials will be destroyed.

Study Population

Patients admitted to the UCMC trauma service are eligible for enrollment.

Inclusion Criteria

- a. Patients with an anticipated length of stay of at least 72 hours
- b. High-risk patients initiated on enoxaparin 30 mg every 12 hours per the existing VTE prophylaxis protocol
 - a. High-risk is defined as patients with a risk assessment profile (RAP) ≥ 5 .¹⁹
 - b. Trauma team VTE prophylaxis protocol contraindications to chemical prophylaxis include
 - i. Intracranial bleeding (e.g., chemical prophylaxis contraindicated within 24 hours of documented stable head computed tomography [CT]),
 - ii. Incomplete spinal cord injury with hematoma within 24 hours post-injury
 - iii. Ongoing hemorrhage
 - iv. Uncorrected coagulopathy
 - v. \geq grade IV liver or spleen injury
 - vi. Intraocular injuries.
- c. Age 18 – 80 years old

Exclusion Criteria

- a. Renal dysfunction (creatinine clearance < 30 mL/min or patients on continuous renal replacement therapy)
- b. Weight < 50 kg or > 150 kg
- c. Platelet count $< 50 \times 10^3$
- d. Allergy to heparin or low molecular weight heparins
- e. Patients on therapeutic anticoagulation at admission or requiring it within 24 hours of admission
- f. Isolated intracranial hemorrhage
- g. Known hyperbilirubinemia (defined as serum bilirubin > 6.6 mg/dL; interferes with the anti-Xa chromogenic assay)

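### Bleeding is counted only while the patient is on enoxaparin, with no window defined around a hold or after a VTE and no reconciliation with intention-to-treat

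*Combined protocol and SAP*

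**What the plan says.** Secondary Endpoints, item 1, compares bleeding between the control and intervention groups. Major bleeding has three criteria, each tied to drug exposure:

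- The first combines a laboratory change with transfusion: "hemoglobin decrease of ≥ 2 g/dL in a 24 hour period requiring ≥ 2 units of packed red blood cells while on enoxaparin".
- The second concerns bleeding inside the skull, whether fresh or extending, and carries the same on-drug condition.
- The third is a return to the operating room: "repeat surgical intervention due to hemorrhage while on enoxaparin".

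Minor bleeding also has three components. A gastrointestinal item and a residual item, "other overt bleeding not characterized a major while on enoxaparin", carry the same qualifier. The remaining one, "interruption of study drug by trauma team", does not, and it does not require a bleed.

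The same item measures "total transfusion requirements after 48 hours until discharge or admission day 28", with no on-drug limit. The statistical paragraph of Data Analysis calls for an intention-to-treat model; the only patients it removes from the VTE and bleeding analyses are those with a change in renal function. Exclusion criterion e covers "Patients on therapeutic anticoagulation at admission or requiring it within 24 hours of admission" and nothing later. Study design describes the trial as non-blinded.

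**The concern.** Bleeding is the risk that the Level of Risk section attaches to higher enoxaparin doses, so this is the trial's main safety comparison. Under the present wording, whether a bleed counts depends on what happens to the drug after assignment.

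The difficult case is an ordinary one. A bleed is suspected, the team holds enoxaparin, and the transfusion or operation follows. The plan does not say whether that patient is still on enoxaparin. The same event could be scored as major, as a minor interruption, as both, or not at all. The treatment arm is known and no bleeding adjudication is described, so the choice could be made with knowledge of the regimen.

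A second gap lies in the other direction. The qualifier names enoxaparin, not the assigned prophylactic regimen. If an on-study VTE were treated with enoxaparin, later bleeds could count against the assigned regimen. VTE is itself a compared outcome, so a VTE difference could then carry into the bleeding comparison.

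**Working it through.** **1. The plan's own figures.** No sample size or rate is given for bleeding. The stated total of 200 rests on AT-III: a difference of 10 points, SD 25, two-sided 0.05 (sidedness assumed), 80% power. Per group, 2 × (1.960 + 0.842)² × 25² / 10² = 98.1, so 99 per group and 198 in all; the t-test version gives 100 per group and 200 in all. The goal anti-Xa comparison (50% vs 77%) gives 49 per arm, or 98 against 100 stated. Both reproduce, and nothing here changes them.

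**2. The bleeding components side by side.**

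| Component | On-drug qualifier | Bleed required | Can be completed after a hold |
|---|---|---|---|
| Major: haemoglobin fall with transfusion | yes | yes | yes, 24-hour fall plus transfusion |
| Major: intracranial | yes | yes | onset may follow a hold |
| Major: repeat operation | yes | yes | yes, the operation |
| Minor: gastrointestinal | yes | yes | onset may follow a hold |
| Minor: drug interruption | no | no | is itself the hold |
| Minor: other overt | yes | yes | onset may follow a hold |

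In the repeat-operation criterion the qualifier can attach to the haemorrhage or to the operation. Under the first reading, a bleed that starts on drug and is operated on after the hold is major. Under the second it is not, and interruption may be the only item met. The haemoglobin criterion has the same two readings.

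**3. Time at issue after the last dose.** Table 1 half-lives are 1.67 h in non-edematous patients (longest 3.92 h, n = 11) and 0.68 h in edematous patients. Five half-lives:

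- 5 × 0.68 = 3.4 h
- 5 × 1.67 = 8.35 h
- 5 × 3.92 = 19.6 h

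At the tabulated central values this is shorter than a 12-hour dosing interval. Only the longest value approaches a day, so a 24 h lag covers every half-life in the table.

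**4. Weight of one event.** 1/100 = 1 point in the control or pooled intervention group; 1/50 = 2 points in a randomized arm.

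**5. Illustration on assumed rates.** Suppose true major bleeding is 2% vs 6% in 100 vs 100, and the same share of bleeds is lost in both groups. The observed difference is (1 − share) × 4 points.

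| Share lost | Observed difference (points) | Approximate power |
|---|---|---|
| 0% | 4.0 | 30% |
| 10% | 3.6 | 28% |
| 25% | 3.0 | 24% |
| 50% | 2.0 | 17% |

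Neither the rates nor the shares come from the documents. If the share lost differs between groups, the difference can move either way.

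**6. Treatment dosing after a VTE.** Table 2's intervention proportions (2.5%, 4.5%, 5.5%, 11%) applied to an arm of 50 give 1.25, 2.25, 2.75 and 5.5 patients with VTE. How many would receive enoxaparin is not stated.

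Bioaccumulation (0.3 IU/mL or more at any assay) needs a further assumption, that protocol assays continue after the switch. The Pharmacokinetic / Safety Information section says "Therapeutic enoxaparin anti-Xa concentrations are between 0.5 – 1.1 IU/mL for 1 mg/kg every 12 hours". Taking that range as an assumed 4-hour level and letting it decay for 4 h by 2^(−4/half-life):

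- half-life 0.68 h: 0.01 to 0.02 IU/mL
- half-life 1.67 h: 0.10 to 0.21 IU/mL
- half-life 3.92 h: 0.25 to 0.54 IU/mL

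The threshold is crossed only near the longest half-life, and only if the 4-hour level exceeds about 0.61 (0.3 / 0.493).

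**The case against.** The strongest reply is that the qualifier belongs to the haemorrhage. On that reading, a bleed that begins on drug is major whenever the transfusion or operation takes place. This is the more natural reading of the repeat-operation criterion and a possible one for the haemoglobin criterion. It stands to this extent: a reader might infer that bleeds completed after a hold are dropped or downgraded, and the documents do not establish that. It does not remove the point, since the plan never states which reading applies and neither reading says how long after the last dose a new bleed still counts.

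Other capture exists. Transfusion is counted to discharge or day 28 whatever the drug status, Data Collection lists bleeding events and drug interruption as separate items, and the medical monitor reviews all adverse events. Serious bleeds would therefore not vanish from the record. But transfused volume does not identify a bleed, and monitor review is not an endpoint rule.

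A reader might also infer that bleeds on treatment-dose enoxaparin will be charged to the prophylaxis arms. The documents do not say how an on-study VTE is treated, and the weekly step-down rules list only the study doses. Applying Table 2's control column (up to 37%) to the arms of 50 would give as many as 18.5 such patients, but those arms are the intervention groups, and step 6 shows the smaller figures.

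Finally, this is an unpowered secondary endpoint in a pilot. That limits the weight of the point, though the change needed is small.

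**Conclusion.** The point holds as a gap in the endpoint definition. The on-drug condition on five of six bleeding components has no stated lag, does not say whether onset or completion governs, and does not separate assigned from treatment dosing. It makes a safety comparison in an open-label trial depend on exposure after assignment, and the plan does not square this with intention-to-treat. Counting an interruption as minor bleeding without a bleed is a separate defect that follows directly from the text.

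The size and direction of any bias cannot be computed: the documents give no bleeding rate for this trial, no share of bleeds that straddle a hold, and no share of VTEs treated with enoxaparin. A reader might conclude that the rule under-counts the most serious bleeds because those are the ones that stop the drug. That is plausible, but no figure in the documents supports it. The post-VTE part is conditional on enoxaparin being used as treatment; its extension to bioaccumulation also needs continued assays and slow elimination. The sample size is unaffected. This is a worthwhile and inexpensive clarification, not a flaw that invalidates the trial.

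**What to change.** These changes concern counting only, not clinical management.

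1. In every bleeding criterion, date the bleed by its onset. Count it from group assignment after assay 1, the same start for control, group 1 and group 2, until a fixed lag after the last enoxaparin dose. A lag of 24 h would cover five of Table 1's longest half-lives (19.6 h); the exact lag is a choice, but it must be set in advance.
2. Add a comparison of all bleeds to discharge or admission day 28 by assigned group, whatever the drug status. This matches the intention-to-treat statement and the existing transfusion window.
3. Report drug interruption separately, which also serves the discontinuation comparison in aim 2. Count it as minor bleeding only when an overt bleed is recorded.
4. Flag bleeds and anti-Xa values of 0.3 IU/mL or more that follow any start of treatment-dose anticoagulation, and show results with and without them. Ending the main count at that switch would be a debatable step away from intention-to-treat; showing both avoids it.

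Cost: endpoint wording, two times from the medication record (last dose, start of treatment anticoagulation), and an onset time added to the bleeding events already collected. The reported major-bleeding rate may rise slightly and the minor-bleeding rate may fall.
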